Once the patient has undergone surgery, the data corresponding to the surgical intervention performed will be collected. Once the period of 7 days has elapsed after the operation and in the absence of complications and pleural drainage, the period of respiratory physiotherapy will begin.

QUALITY OF LIFE ASSESSMENT

The health questionnaire SF-36 (Short Form Health Survey) will be used. This questionnaire is used in medical research, mental health research and health-related research in general. It provides an overview of a person's state of health, with the advantage that it is easy and quick to fill in and simple to evaluate. Similarly, by allowing numerical assessment of different aspects of a person's health, it can be used to assess the health status of the individual.

The questionnaire is an excellent tool for any health-related research. It contains 36 questions that address different aspects related to the daily life of the person filling in the questionnaire. These questions are grouped and measured in 8 sections that are assessed independently and give rise to 8 dimensions measured by the questionnaire.

The eight dimensions are:

1. Physical functioning.
2. Limitation due to physical problems.
3. Body pain.
4. Functioning or social role.
5. Mental health.
6. Limitation due to emotional problems.
7. Vitality energy or fatigue.
8. General perception of health. (Annex 1).

In 1991, the International Quality of Life Assessment Project (IQOLA) was initiated, consisting mainly of adapting and testing the cross-cultural applicability of a generic instrument called the Short Form 36 Health Survey (SF-36) (27).

The Spanish version of the SF-36 is one of the most widely used generic instruments in Spain, both in descriptive studies that measure the impact on HRQOL in different patient populations and for the evaluation of therapeutic interventions (28).

PAIN ASSESSMENT

The tools necessary to make a correct assessment of pain. In this sense, two ways of measuring pain will be established:

1. Self-reports, where the visual analogue scale (VAS) will be the basic measurement tool. Pain will be marked on a scale from 0 (no pain) to 10 (maximum possible pain).
2. The standardised tests, as an objective of the study, also aim to analyse sensory, affective and behavioural aspects of pain in these patients, which is why the Mc Gill test will be the tool to be taken into account (Appendix 2).

ASSESSMENT OF RESPIRATORY FUNCTION

The different respiratory parameters will be measured by spirometry (Siebel spirometer): Forced Vital Capacity (FVC); Forced Expiratory Volume of the first second (FEV₁); FEV₁/FVC (Tiffeneau Index).

COST ANALYSIS

Activity times shall be measured in two groups of patients. In all cases, the recovery time and return to normal life will be established. A study of the costs of visits and physiotherapy treatment of these patients until their return to normality prior to the intervention will be carried out.

STATISTICAL STUDY

Data collection will be carried out over a period of three years. There are no reliable data to allow statistical calculation of the sample size, but it is estimated that 30 patients are needed for each of the subgroups described, giving a total sample size of 180 patients.

This is a prospective, randomised, longitudinal study.

STATISTICAL ANALYSIS

Quantitative variables will be described by means of centralisation and dispersion indices: mean, standard deviation and range. The hypothesis of normality of the variables will be verified using the Kolmogorov-Smirnov test for a single sample. Qualitative variables will be treated by analysing the absolute frequency of occurrence of each of the categories, as well as the relative frequencies. Categorical data will be compared using the χ^2 test or Fisher's exact test when necessary. RANOVA will be used when more than 2 means of related variables are to be compared. Student's t-test should be used when comparing 2 related or independent means. In addition, multivariate analysis (multiple linear and logistic regression) will be used for the correct modelling of the relationship between variables. The accepted level of statistical significance is $p<0,05$. Data will be analysed using the statistical package SPSS version 15.0 (SPSS, Inc, Chicago).

REQUEST FOR EVALUATION BY THE CENTRE'S ETHICS COMMITTEE

Immediate application shall be made to the Centre's Research Ethics Committee.

APPLICABILITY OF THE RESULTS

The applicability of the results will be carried out in the Rehabilitation Services that have a Respiratory Physiotherapy unit.

From an economic point of view.

1. The TENS analgesia technique is a low-cost technique and, according to the existing literature, it is effective in the process under study.

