[name] [name]. Tasks: carrying out interventions, data collection, participation in the production of publications and presentations.

[name] [name]. Tasks: carrying out interventions, data collection.

[name] [name]. Tasks: assessment and design of respiratory tests, participation in publications and presentations.

[name] [name]. Tasks: assessment and design of respiratory tests, participation in publications and presentations.

[name] [name]. Tasks: participation in the design of the work, data collection and participation in the production of publications and presentations.

WORK PLAN

1. Patient recruitment and study of patients: January 2015 to December 2017.

2. Collection of data to complement the Clinical History.

Step 3. Introduction to the study. Explanation of the procedure. Signed consent form.

Step 4. Measurement of parameters:

1. Measurement of pain, Mc Gill test.
2. Measurement of respiratory parameters. Spirometry.
3. Quality of Life Measure. SF-36.
4. Measured with the Minnesota Multiphasic Personality Inventory.
5. Counting days of treatment.

Step 5. Start of the respiratory physiotherapy programme. It will be carried out in the respiratory physiotherapy unit of the University Hospital of Gran Canaria [name]. Patients will be divided into the two groups described above and will be included in the treatment programme. The sequence for the intervention group will be as follows:

1. Explanation of the programme.
2. Placement of external analgesic measures (TENS). The frequency of application would be 100 hz as this is the type of application that produces the greatest analgesia.
10,11,12,13
3. Implementation of the treatment regimen, for x days.
4. In the middle of the programme, measurement of all the above

parameters. Step 6. Continuation of the physiotherapy programme.

Step 7. Completion of the physiotherapy programme. Measurement of all parameters again, plus accounting of treatment days.

In the control group, the same would be done but no intensity would be given when applying TENS. The steps to follow would be the same.

ECONOMIC STUDY

Within the economic study that will define this work, we will highlight two fundamental points:

Portable spirometer brand..... 1500 Euros.

Publication of results..... 1500 Euros.

Attendance at Conferences and Scientific Conferences 750 Euros.

Publication in scientific journals in the sector..... 750 Euros.

TOTAL 3000 Euros.

BIBLIOGRAPHY

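### RANOVA across three measurement times uses only patients with all three values; a mixed model would use every observed visit and is valid under missing at random

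*Protocol*

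**What the plan says.** The statistical study section describes the design: "This is a prospective, randomised, longitudinal study". The work plan sets three rounds of measurement:

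- Before the programme: "Step 4. Measurement of parameters", covering the McGill test, spirometry and SF-36 among others.
- Midway, in Step 5: "In the middle of the programme, measurement of all the above" parameters.
- At the end, in Step 7: "Completion of the physiotherapy programme. Measurement of all parameters again, plus accounting of treatment days".

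For such data the statistical analysis section states: "RANOVA will be used when more than 2 means of related variables are to be compared". Two other provisions bear on the point. For pairs of means, "Student's t-test should be used when comparing 2 related or independent means". For modelling, "multivariate analysis (multiple linear and logistic regression) will be used for the correct modelling of the relationship between variables". No mixed model is named. The software line reads: "Data will be analysed using the statistical package SPSS version 15.0".

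The protocol does not say which of these methods compares TENS with control, and it gives no dropout rate.

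**The concern.** RANOVA is the only listed method that takes the three visits together. In its classical form it works on complete rows, so a patient with a start and a middle value but no final value contributes nothing. The protocol need not state this deletion, because it comes with the method.

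Two things are at stake. The first is information, since observed scores are thrown away. The second is bias: if patients who miss a visit differ in their earlier scores from those who stay, the completers are a selected group, and if the selection differs by arm, a contrast between arms among completers no longer compares the randomised groups. Programme length is left open, and the third objective expects effective physiotherapy to shorten outpatient care. A link between leaving, recovery and arm is therefore plausible, but it is inferred from the design and not stated.

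The criticism is of a method that the protocol names. The absence of a missing-data policy, which may sit in a SAP that is not shown, is not the point.

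**Working it through.** **The plan's own figure.** Three surgical groups x two subgroups x 30 patients = 180, as stated. The 30 has no derivation to check.

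**How many patients stay complete (assumed rates).** If a fraction m is missing independently at each of the middle and final visits, 180 x (1 - m)² patients have all three values:

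- m = 10%: 180 x 0.81 = 145.8, about 146.
- m = 15%: 180 x 0.7225 = 130.05, about 130.

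**Bias, by simulation. Every input below is assumed; none comes from the protocol.**

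- 90 patients per arm, 4,000 replicates, three visits, SD 1, lower score better. Correlation between adjacent visits is r = 0.5 or 0.7, and r² between first and last.
- True arm difference 0, -0.25 and -0.50 at start, middle and end. The true arm main effect is (0 - 0.25 - 0.50)/3 = -0.25.
- Only the end value can be missing. Log-odds of missing = -1.4 - b x (score minus its control mean), with b = 1 or 2; b = 0 gives 1/(1 + e^1.4) = 20% missing.
- The score driving loss is the observed middle score (missing at random) or the unseen end score (missing not at random). Under opposite rules, low-pain patients leave the TENS arm and high-pain patients leave control.
- Complete-case estimate: the arm difference among patients with all three values.
- Likelihood estimate: end score regressed on start, middle and arm among those observed, predicted for everyone and averaged by arm. This is the maximum-likelihood solution for this missing pattern.

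Ranges run over both values of r and b:

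| What drives loss | Missing, TENS / control | Complete cases: end; change; main | Likelihood: end; change; main |
|---|---|---|---|
| Nothing | 20% / 20% | -0.50 to -0.51; -0.50; -0.25 | -0.50 to -0.51; -0.50; -0.25 |
| Middle score, same rule | 28/24% to 37/30% | -0.45 to -0.48; -0.50; -0.19 to -0.23 | -0.50 to -0.51; -0.50; -0.25 |
| Middle score, opposite rules | 28/24% to 37/30% | -0.28 to +0.08; -0.50; +0.04 to +0.41 | -0.50 to -0.51; -0.50; -0.25 |
| Unseen end score | 32/24% to 44/30% | -0.34 to -0.43; -0.38 to -0.46; -0.14 to -0.21 | -0.37 to -0.46; -0.37 to -0.46; -0.20 to -0.24 |

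The complete-case difference in change is unbiased in the second and third rows because start and end have the same correlation with the middle score. Selection on the middle score shifts both equally and cancels. With unequal correlations (three patterns between 0.5 and 0.7, 77% to 83% kept, moderately opposite rules) it ran from -0.43 to -0.57. In those runs the end difference was -0.25 or about -0.71, depending on which arm lost which patients, so bias can go either way.

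**Precision.** At 20% missing completely at random, the SD of the estimated change difference is 0.199 (likelihood) against 0.210 (complete cases) for r = 0.5, a ratio of 0.95. For r = 0.7 it is 0.161 against 0.169, again 0.95. The gain is not universal: under strong opposite rules the likelihood end estimate has the larger SD (0.197 against 0.177 for r = 0.5), the price of removing the bias.

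**The case against.** The strongest reply is that the protocol never makes RANOVA the arm comparison. Its wording concerns related means, which is a within-patient comparison, while two independent means go to the t-test and regression is also available. Neither needs the middle value. This stands, and it rules out one tempting inference: that the trial's treatment effect will be estimated by RANOVA and will be biased. It does not rescue the method, because a t-test or regression on the final value also uses only patients who have that value.

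A reader might also infer that early recoverers are the ones who lack the last measurement. The work plan does not support that. The last measurement is taken when the programme is completed, so someone who finishes early is still measured. What that raises is a question of visit timing.

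Third, the harm depends entirely on visits being missed, and no rate is given. With complete data nothing is lost on this point. The large biases need leaving rules that run in opposite directions by arm, and nothing in the protocol says that they do. This stands as a limit on size.

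Finally, one might conclude that a mixed model removes both the loss of data and the bias. It does not. It is unbiased when loss depends on observed scores; when loss depends on unseen recovery it remains biased. There it was somewhat closer to the truth for the end difference and the main effect, but complete cases were closer by up to about 0.01 SD for the change difference. Nor does it restore the 34 to 50 incomplete patients (180 - 146 and 180 - 130). The lack of an allowance for loss in the 180 is a separate sample-size matter.

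**Conclusion.** The point holds in a limited form. For a design with three visits the protocol names a method that discards every patient with a gap. It can distort the end difference and the arm main effect if gaps depend on earlier observed scores. A likelihood-based mixed model is the better choice: for those two contrasts it was unbiased under missing at random where complete cases were not, and no further from the truth in the other scenarios.

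The size cannot be fixed from the protocol. Under the assumed mechanisms it runs from slight (0.02 to 0.05 SD off a true -0.50 with the same rule in both arms) to large (the effect cut to -0.28 or reversed to +0.08 with opposite rules). The efficiency gain is about 5% in SD at 20% missing completely at random. These figures rest on assumed dropout, correlations and effects, and on RANOVA being used for an arm contrast, which the protocol leaves open.

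**What to change.** Replace the RANOVA sentence with a linear mixed model for repeated measures:

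- Outcomes: the middle and final values.
- Fixed effects: arm, visit, arm x visit, the start value of the same measure and surgical group.
- Covariance: unstructured across visits.
- Patients: all randomised patients with at least one value after the start, analysed in the arm assigned.
- Estimate reported: the arm difference at the final measurement, with its confidence interval.

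State that the analysis is valid under missing at random. Add a sensitivity analysis for leaving that depends on unobserved recovery, for example by shifting the unobserved final values by a range of amounts, separately by arm. Report how many patients lack each visit, by arm, including those with no value after the start.

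The cost is a change of wording and slightly more analysis work; no new data are needed. Confirm that the named software version fits the model as specified. The change does not deal with the timing of the completion visit: the work plan leaves the number of treatment days open, and a model on nominal visits treats final values taken at different times as the same occasion. That needs its own resolution.

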1. Physiotherapy techniques are an effective element of pain control in the postoperative chest surgery patient.
2. The quality of life of postoperative chest surgery patients improves with the application of analgesic physiotherapy techniques.
3. Respiratory parameters improve in a shorter time if pain control is carried out during respiratory physiotherapy sessions.
4. As a result, the healthcare expenditure involved in caring for these patients decreases considerably.

The objectives of this work are therefore defined as follows:

Objective one: To demonstrate that physical pain control using transcutaneous electrostimulation (TENS) results in effective physiotherapy for the improvement of respiratory capacities.

Objective two: To demonstrate that improvement in respiratory capacity improves patients' quality of life.

Objective three: To demonstrate that effective physiotherapy results in less time spent in outpatient care, leading to a reduction in the case-mix of rehabilitation and a reduction in the health care costs associated with this intervention.

HYPOTHESIS

Physical pain control using transcutaneous electrostimulation (TENS) in patients who have undergone chest surgery allows effective physiotherapy that improves respiratory capacity and quality of life and reduces health care costs.

MATERIAL AND METHOD

DEFINITION OF THE STUDY

This is a prospective, randomised study in which the aim is to study the value of an analgesic technique (TENS). The study will be carried out on patients undergoing thoracic surgery for pleural, pulmonary or mediastinal procedures of varying complexity. Patients will be recruited once the immediate postoperative period has passed, with a deadline of 7 days after the operation for inclusion in the study. There will be three groups of patients:

Group 1.- Patients treated with anterior, lateral or axillary thoracotomy.

Group 2.- Patients treated with videothoracoscopy with three or more entry doors and/or with mini-thoracotomy assistance.

Group 3.- Patients treated with videothoracoscopy with one or two entry doors.

Inclusion criteria

Patients treated with each of the interventions described and who are between 18 and 80 years of age.

Signed informed consent to participate in the study. Exclusion

criteria

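### No primary outcome, time point or TENS v control comparison is named among about 14 outcomes, all tested at p<0.05, and the only test named for two independent means is an unadjusted t-test

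*Protocol*

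**What the plan says.** **Outcomes.** OBJECTIVE gives four points to demonstrate; the first is that "Physiotherapy techniques are an effective element of pain control in the postoperative chest surgery patient". Objective one, in the same section, instead concerns whether TENS "results in effective physiotherapy for the improvement of respiratory capacities". Objective three is "To demonstrate that effective physiotherapy results in less time spent in outpatient care". HYPOTHESIS states that effective physiotherapy "improves respiratory capacity and quality of life and reduces health care costs". PAIN ASSESSMENT gives the VAS a central place among self-reports, but the Step 4 list in WORK PLAN names only the McGill test for pain.

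**Time points.** WORK PLAN measures the parameters before treatment, in the middle and at the end of a programme whose number of days is left open. Neither follow-up measurement is called primary.

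**Comparison.** Patients are randomised to TENS or control within three surgical groups. STATISTICAL STUDY says "it is estimated that 30 patients are needed for each of the subgroups described", 180 in total. COST ANALYSIS and WORK PLAN Step 5, by contrast, speak of two groups of patients.

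**Analysis.** For two means, "Student's t-test should be used when comparing 2 related or independent means". RANOVA is named for more than two related means, and "multivariate analysis (multiple linear and logistic regression) will be used for the correct modelling of the relationship between variables". A single threshold of p<0.05 covers every test, with no allocation over outcomes, times or groups.

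**The concern.** Primary outcome, time point and main comparison are choices a protocol makes itself. This one sets its tests, threshold and sample size without saying what they apply to. List order does not help, because pain leads one list and respiratory capacity the other.

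Pooled or within-group is a real scientific choice here. The protocol's own review of earlier work (TRANSCUTANEOUS ELECTRICAL STIMULATION) reports a study in which TENS helped after less painful thoracic operations and not after painful ones.

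Two things are at stake. With many unranked outcomes, a reader cannot tell an intended positive result from a chance one. And the smallest effect the trial can reliably detect depends on a choice left open. A lesser point is that an unadjusted t-test on one follow-up value ignores pre-treatment data that are already collected, so a moderate real effect is easier to miss.

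**Working it through.** **The plan's own figure.** 3 surgical groups × 2 subgroups × 30 = 180, as stated. The 30 cannot be derived: the protocol gives no effect, SD or power and says there were no reliable data for a calculation.

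**Number of outcomes.** 8 SF-36 dimensions + VAS + McGill (as one score) + FVC, FEV1 and FEV1/FVC + treatment days = 8 + 1 + 1 + 3 + 1 = 14. Adding recovery time, cost and the personality inventory, one score each, gives 17.

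**Chance of at least one false positive** (no TENS effect, two-sided 5% assumed):
- Independent outcomes: 1 − 0.95^14 = 0.512; with 17 outcomes, 1 − 0.95^17 = 0.582.
- 14 outcomes with an assumed common correlation of 0.3, 0.5 or 0.7 (simulated): 0.44, 0.35 or 0.25.
- Each surgical group tested separately: 1 − 0.95^42 = 0.884 if independent. At correlation 0.5 within a group, 1 − (1 − 0.347)^3 = 0.72.
- Two follow-up times instead: 1 − 0.95^28 = 0.762 if independent.

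The independence figures are upper ones, since the outcomes overlap; FEV1/FVC, for example, is computed from two others.

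**Detectable effect, 80% power, unadjusted.** By the normal approximation d = (1.960 + 0.842) × √(2/n): 0.418 SD at n = 90 per arm and 0.723 SD at n = 30. With the exact t distribution: 0.420 and 0.736 SD.

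**Power at an assumed true effect of 0.4 SD.** Noncentral t with noncentrality d√(n/2): 0.4 × √45 = 2.68 pooled and 0.4 × √15 = 1.55 within a group. Adjusting for a baseline with correlation r divides this by √(1 − r²), at a cost of 3 degrees of freedom pooled (baseline and surgical group) or 1 within a group. The protocol gives no r, so a range is shown.

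| Analysis | 90 v 90 | 30 v 30 |
|---|---|---|
| t-test on one follow-up value | 76% | 33% |
| Adjusted, r = 0.3 | 80% | 36% |
| Adjusted, r = 0.5 | 87% | 42% |
| Adjusted, r = 0.7 | 96% | 57% |
| t-test, 5% split over three groups | not applicable | 19% |

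Simulated regression with baseline and three surgical groups agrees for the pooled case: 0.795, 0.862 and 0.966. At effects of 0.3 or 0.5 SD the unadjusted t-test has 52% or 92% power pooled, and 21% or 48% within a group.

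**Ignoring surgical group in the pooled t-test.** If group means differ by ±0.25 or ±0.5 SD (assumed), power falls from 76% to 75% or 71%. Type I error is not inflated. If surgical group explains an assumed 10% to 30% of the variance, it falls to between 4.0% and 2.0%.

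**The case against.** **The t-test is not an error, and covariates and multiplicity often belong in an analysis plan that is not shown.** The first part stands: the test is valid, and adjustment is a gain in efficiency rather than a correction. Details of adjustment and error control could sit elsewhere. The primary outcome, its time point and the main comparison could not reasonably be left out of the protocol.

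**The power loss assumes a t-test on one follow-up value.** This is a fair limit. The study is called longitudinal, and RANOVA and regression are planned. A t-test on change from the pre-treatment value would also fit the text. Its SD is √(2(1 − r)) times that of the raw value, so at 0.4 SD and 90 v 90 its power is 62%, 76% or 93% at r = 0.3, 0.5 or 0.7. Each is below the adjusted 80%, 87% or 96%. None of these methods is tied to the TENS v control comparison.

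**Some text favours a pooled comparison.** The hypothesis concerns chest surgery patients generally, and COST ANALYSIS and WORK PLAN mention two groups. That is so, but sizing each subgroup at 30 points the other way, which confirms that the choice is open.

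**The count of 14 is selective.** It omits recovery time, cost and the second follow-up time, and takes McGill as one score although Annex 2 has several. Counting these would only raise the false-positive chance.

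**No text claims that within-arm tests show a TENS effect.** True; the related request below is a precaution, because paired t-tests and RANOVA are both listed.

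**Conclusion.** The concern holds and should be fixed. No outcome, time point or comparison is designated, so no result can be identified as the planned test. Across 14 outcomes in one comparison the chance of some false-positive claim is about 35% to 51%, for correlations between 0.5 and zero. The detectable effect is 0.42 SD or 0.74 SD depending on whether groups are pooled. The missing baseline adjustment is secondary: 4 to 20 percentage points of power in the pooled case (76% against 80% to 96%), and only if the t-test on one follow-up value is the main analysis. Effect sizes, correlations, group differences and two-sidedness are assumptions; the protocol gives none of them. Randomisation and data remain usable.

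**What to change.** In STATISTICAL ANALYSIS:

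1. Name one primary outcome, one time point and one comparison (pooled or within surgical group), tested at 5%. Treat all other outcomes as secondary. If the comparison is within groups, say which group is primary or how the 5% is split over three. State whether the choice preceded any look at outcome data; if it did not, label it post hoc.
2. Make the already planned linear regression the TENS v control analysis, adjusted for the Step 4 value of the same variable, and for surgical group if groups are pooled. VAS may be chosen as primary, but it is not in the Step 4 list, so adjust it for surgical group only unless a baseline VAS was recorded. The same holds for treatment days, recovery time and cost, which have no baseline.
3. State that within-arm paired t-tests and RANOVA time effects are not evidence of a TENS effect.
4. If programme completion (Step 7) is the time point, report days to Step 7 by arm, because Objective three expects TENS to shorten the programme. Do likewise for the mid-programme measurement. This shows any difference in timing between arms but does not remove it.
5. Report effects by surgical group with confidence intervals, as descriptive if the pooled comparison is primary.

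The cost is wording, with no new patients or measurements; fewer outcomes can then be called significant. Recruitment was planned for January 2015 to December 2017 and the document is dated March 2021, without saying whether data had been seen. If they had, the change makes the position honest but cannot protect against selective choice, and the result is weaker evidence.
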